### **Caregiver Version**

**[The following two items are being evaluated as observer-reported outcome (ObsRO) items for children that are not able to report on ease of use or remaining doses].**

Please answer the following question based on what you observed when your child used the study inhaler (called the ELLIPTA) at home. Choose only one response for each question.

1. How easy was it for your child to use the ELLIPTA inhaler?

- Very easy
- Easy
- Difficult
- Very difficult

2. How easy was it for your child to tell how many doses were left in the ELLIPTA inhaler?

- Very easy
- Easy
- Difficult
- Very difficult

**[The below items are being evaluated as PRO items based on the experience of the caregiver].**

Please answer the following questions based on your experiences while your child was using the study inhaler (called the ELLIPTA) at home. Choose only one response for each question.

1. How easy was it for you to tell how many doses were left in the ELLIPTA inhaler?

- Very easy
- Easy
- Difficult
- Very difficult

2. If your child's current daily inhaled asthma medication was available in the ELLIPTA inhaler, how likely would you be to request the ELLIPTA inhaler from your child's doctor?

- Very likely
- Likely
- Unlikely
- Very unlikely

## **APPENDIX C: INTERVIEW GUIDE**

## **Interview Discussion Guide: Pediatric Inhaler Ease of Use**

NOTE: This guide is to be utilized as a topic guide, to encourage spontaneity of responses and foster a relaxed tone throughout the discussion. The guide is not intended to be followed in a verbatim question format. Discussion starts only after informed consents, parental permission forms and assents are completed.

### **I. Introduction**

#### **A. Introductions**

*"Hi, my name is \_\_\_\_\_ and I work for a company called RTI Health Solutions. What is your first name?"*

#### **B. Explain the purpose of the interview**

*"We are doing a study to learn about what kids think of the inhalers they use for asthma. We want to figure out the best way to ask kids about using an inhaler. We will be talking to other kids like you and their parents to make questions that will be easy to answer.*

*First, I am going to ask you some questions about the inhaler that you use for your asthma and what you think about it. Then I'm going to ask you to listen to [or read for children 8-11] some questions and let me know what you think about them. There are no right or wrong answers to these questions. I just want you to tell me what you really think! When we are done, I am going to ask your [mom, dad, other caregiver] some questions about your inhaler and have them answer some questions to tell me how we can make those questions better. [Caregiver/parent will be asked to sit behind the child to avoid influencing the child's responses during the child interview portion. For the caregiver portion, there will be quiet activities such as paper and crayons available for the child while the interviewers are speaking with the caregiver].*

*Do you have any questions for me before we get started?*

*OK, let's begin..."*

### **II. Discussion with Child: Warm-up (Same questions for all children)**

- Can you tell me about the inhaler that you use every day? Not the inhaler that might be called a "rescue" inhaler (for when you are having trouble breathing), but the one that you use all the time.
- What do you call this inhaler?
- What do you think about using [child's name for inhaler]? Is it hard to use? Why? Do you like to use it? Why (or why not)?
- Do you remember who taught you how to use [child's name for inhaler]? Was it hard to learn how to use it?
- Does anyone help you when you use it?
- How do you remember to use it every [night, morning or night and morning]?
- Do you know when the [child's name for inhaler] is almost out of medicine? How?

- Can you tell me how you take your medicine? Can you pretend you have your [child's name for inhaler] with you now and show me how you use it? How do you get the inhaler ready? After it is ready, what do you do to use it? What else do you have to do when you use your inhaler?
- Thank you for telling me about your [child's name for inhaler]. Now I want to ask you some questions about using an inhaler. When you are answering the questions, I want you to think about the inhaler that you just told me about we just talked about [Note: for the purposes of cognitive debriefing, replace ELLIPTA with the child's name of his/her maintenance inhaler, do this verbally for the children in the 5-7 age range, for the children that are 8-11 can update "ELLIPTA" on the questionnaire to the name that the child calls their inhaler (if just "inhaler" can put one line through ELLIPTA)].

#### Debrief (Children 5-7):

*Instructions: I will read the question and answers to you. Then I will ask you to choose the answer that matches what you thought about using the [child's name for inhaler] at home. Do you have any questions for me?"*

1a. How easy is it to use the [ELLIPTA] inhaler?

- Very easy
- Easy
- Hard
- Very hard

[Interviewer notes the response selected by the child].

- Could you please tell me what it is about [child's name for inhaler] that makes you say it's [child's answer] to use? What did you have to think about to answer?
- Was it hard to understand my question? Why? Was it hard to choose an answer? Why?
- What would it be like if it was [opposite of what child chose – hard or easy]?
- Is easy and very easy the same for you or are they different? What things are easy for you? What things are very easy for you?
- Is hard and very hard the same for you or are they different? What things are hard for you? What things are very hard for you?

Thank you, now I have another question to ask you.

1b. Is it easy to use the [ELLIPTA] inhaler?

- Yes
- No

- What makes you answer [child's response] to this question? What did you have to think about?
- Is this question the same or different than the one we just talked about?
- Was this question easier or harder for you to answer? Why?

Thank you, now I am going to ask another question, but this time I have a different way for you to tell me your answer [interviewer provides child with sheet that has the item and responses, interviewer reads the question and the response under each face, when pointing to the face and asks the child to circle the face that matches their answer].

1c. How easy is it to use the [ELLIPTA] inhaler?

Very easy

Easy

Hard

Very hard

- Do you think the faces make it easier to answer the question? Why?
- [Only ask if a different response from 1a was chosen] You circled [child's response]. Why did you choose that answer?
- If you had to tell me about [select a face], what words would you use? What feeling does the face make you think of? Why?
- Which of the three questions that I asked you was the easiest to answer? Why?

Thank you, now we have three more questions for you before we talk to your [mom, dad, other caregiver].

2a. How easy is it to tell how many puffs are left in the [ELLIPTA] inhaler?

- Very easy
- Easy
- Hard
- Very hard

[Interviewer notes the response selected by the child].

- Could you please tell me what it is about [child's name for inhaler] that makes you say it's [child's answer] to tell how many puffs are left?
- What does a puff mean?
- What did you have to think about to answer?
- Was it hard to understand my question? Why? Was it hard to choose an answer? Why?
- What would it be like if it was [opposite of what child chose – hard or easy] to tell how many puffs were left?
- Is easy and very easy the same for you or are they different? What things are easy for you? What things are very easy for you?
- Is hard and very hard the same for you or are they different? What things are hard for you? What things are very hard for you?

Thank you, now I have another question to ask you.

2b. Is it easy is it to tell how many puffs are left in the [ELLIPTA] inhaler?

- Yes
- No

[figure not shown]
- What makes you answer [child's response] to this question? What did you have to think about?
- Is this question the same or different than the one we just talked about?
- Was this question easier or harder for you to answer? Why?

Thank you, now I am going to ask another question where you circle your answer [interviewer provides child with sheet that has the item and responses, interviewer reads the question and the response under each face, when pointing to the face and asks the child to circle the face that matches their answer].

2c. How easy is it to tell how many puffs are left in the [ELLIPTA] inhaler?

[figure not shown]
Very easy

Easy

Hard

Very hard

- Do you think the faces make it easier to answer the question? Why?
- [Only ask if a different response from 1a was chosen] You circled [child's response]. Why did you choose that answer?
- If you had to tell me about [select a face], what words would you use? What feeling does the face make you think of? Why?
- Which of the three questions that I asked you was the easiest to answer? Why?

Thank you, is there anything else about how easy or hard it is to use your inhaler that you think I should know? Okay, now we will ask your (mom, dad, other caregiver) a few questions.

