#### Debrief (children 8-11):

I would like you to read and answer a few questions for me. When you read them, I would like you to read them out loud. I would also like to tell me what you are thinking about when you decide on an answer. There are no right or wrong answers, I just want to understand how you think about the question.

[Provide the child the child with the first question]

Let's start with the first sentence:

*Please choose one answer.*

- What does that sentence mean to you? Was it hard to understand?

Let's go on to the question, can you read the question out loud?

1a. How easy is it to use the [ELLIPTA] inhaler?

Can you read each of the answers below the question out loud and choose a response?

- Very easy
- Easy
- Hard
- Very hard

- Could you please tell me what it is about [child's name for inhaler] that makes you say it's [child's answer] to use? What did you have to think about to answer?
- Was it hard to understand my question? Why? Was it hard to choose an answer? Why?
- What would it be like if it was [opposite of what child chose – hard or easy]?
- Is easy and very easy the same for you or are they different? What things are easy for you? What things are very easy for you?
- Is hard and very hard the same for you or are they different? What things are hard for you? What things are very hard for you?

Thank you, now I have another question for us to look at.

Can you read this question out loud?

1b. Is it easy to use the [ELLIPTA] inhaler?

Can you read each of the answers below the question out loud and choose a response?

Yes  
 No

- What makes you answer [child's response] to this question? What did you have to think about?
- Is this question the same or different than the one we just talked about?
- Was this question easier or harder for you to answer? Why?

Thank you, now I am going to show you another question. Can you read this question out loud?

1c. How easy is it to use the [ELLIPTA] inhaler?

Can you read each of the words below the pictures of faces out loud and choose a response?

Very easy

Easy

Hard

Very hard

- Do you think the faces make it easier to answer the question? Why?
- [Only ask if a different response from 1a was chosen] You circled [child's response]. Why did you choose that answer?
- If you had to tell me about [select a face], what words would you use? What feeling does the face make you think of? Why?

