Let's look back at all 3 of these questions. Which one was the easiest to answer? Why? Which question did you like the best? Why?

Thank you, now we have three more questions for you before we talk to your [mom, dad, other caregiver].

Can you read this question aloud?

2a. How easy is it to tell how many puffs are left in the [ELLIPTA] inhaler?

Can you read the answers under the question aloud and choose an answer?

- Very easy
- Easy
- Hard
- Very hard

- Could you please tell me what it is about [child's name for inhaler] that makes you say it's [child's answer] to tell how many puffs are left?
- What does a puff mean?
- What did you have to think about to answer?
- Was it hard to understand my question? Why? Was it hard to choose an answer? Why?
- What would it be like if it was [opposite of what child chose – hard or easy] to tell how many puffs were left?
- Is easy and very easy the same for you or are they different? What things are easy for you? What things are very easy for you?
- Is hard and very hard the same for you or are they different? What things are hard for you? What things are very hard for you?

Thank you, now I have another question to ask you.

2b. Is it easy is it to tell how many puffs are left in the [ELLIPTA] inhaler?

Can you read the answers under the question aloud and choose an answer?

- Yes
- No

- What makes you answer [child's response] to this question? What did you have to think about?
- Is this question the same or different than the one we just talked about?
- Was this question easier or harder for you to answer? Why?

Thank you, now we have one more question for you.

Can you read the question out loud?

2c. How easy is it to tell how many puffs are left in the [ELLIPTA] inhaler?

Can you read each of the words under the pictures of the faces out loud and choose an answer?

Very easy

Easy

Hard

Very hard

- Do you think the faces make it easier to answer the question? Why?
- [Only ask if a different response from 1a was chosen] You circled [child's response]. Why did you choose that answer?
- If you had to tell me about [select a face], what words would you use? What feeling does the face make you think of? Why?

Let's look back at all 3 of these questions. Which one was the easiest to answer? Why? Which question did you like the best? Why?

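### In both age modules the words-versus-faces follow-up at item 2c is triggered by item 1a instead of item 2a; the fixed order of the answer formats is a lesser point, to be stated as a limitation

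*Combined protocol and SAP*

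**What the plan says.** Appendix B offers three alternative answer formats for each of two items. Item 1 is about how easy the inhaler is to use, and item 2 about how easy it is to tell how many puffs remain. Version a is a four-label word scale, b is yes/no, and c puts the same four labels under faces.

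In Appendix C, both debrief modules (ages 5-7 and 8-11) script a, then b, then c, for item 1 and again for item 2. After 1c, and again after 2c, a follow-up asking why the child chose the answer is conditional: "Only ask if a different response from 1a was chosen". The reference to 1a is the same in all four places.

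After the three versions the younger children are asked "Which of the three questions that I asked you was the easiest to answer? Why". The older children are asked "Which one was the easiest to answer? Why? Which question did you like the best? Why". Section 3.1 calls the guide standardized, for consistency across interviews, while the note at the head of Appendix C says "The guide is not intended to be followed in a verbatim question format". Section 4 makes problems with wording or response options a goal of the first set of interviews, and asks the final report for the rationale behind item changes. Section 5 does not mention the order of the formats.

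**The concern.** The conditional follow-up exists to find out why a child answers the same question differently once faces are added. At 1c it does that. At 2c it compares an answer about puffs left with an answer about using the inhaler, two different attributes on which a child may well give different ratings. The comparison of interest, 2c with 2a, is never the trigger. Where the rule misses, the discrepancy can still be seen in the recorded answers, but its reason is not sought. In the 5-7 module this is the only scripted question at 2c that asks why the child picked that answer.

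The lesser concern is order. When a child reaches c, the same content has been answered twice and the meaning of the labels has been discussed at length under a. A preference for a format, or agreement between words and faces, may come from the format, from its place in the sequence, or from that earlier discussion.

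**Working it through.** **Inputs.** Sections 3.1 and 3.4: two sets of about 8 dyads. Appendix C: item order, four response labels on the word and faces scales, and the follow-up rule. The study has no hypothesis test, so no error rate or power enters.

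**The plan's own figure.** 2 × 8 = 16 dyads and 16 × 2 = 32 participants, as stated.

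**The rule at 2c.** As written, probe if 2c differs from 1a. The matching comparison is to probe if 2c differs from 2a. With four labels each for 1a, 2a and 2c there are 4 × 4 × 4 = 64 patterns.

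| Pattern | Count | Rule as written | Result |
|---|---|---|---|
| 2c equals both 2a and 1a | 4 | silent | right |
| 2c differs from both 2a and 1a | 4 × 3 × 3 = 36 | fires | right |
| 2c equals 2a, differs from 1a | 4 × 3 = 12 | fires | consistent answer probed |
| 2c equals 1a, differs from 2a | 4 × 3 = 12 | silent | discrepancy missed |

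The total is 4 + 36 + 12 + 12 = 64, with 40 handled correctly. Of the 12 + 36 = 48 patterns with a discrepancy, 12 are missed. Of the 4 + 12 = 16 consistent patterns, 12 are probed.

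Examples, each with 1a very easy and 2a hard: if 2c is very easy, the faces have moved the answer and no follow-up is asked. If 2c is hard, words and faces agree and the follow-up is asked.

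**Order.** As scripted, for 16 children and a guide left unchanged in the second set (an assumption, since section 3.4 allows refinement), the word scale comes first for 16 and faces come last for 16. Format and position coincide completely, and more interviews in the same order would not separate them.

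**What the script asks about ease.** There are 2 modules × 2 items × 3 formats = 12 presentations. The wording "Was it hard to understand my question? Why? Was it hard to choose an answer? Why" is scripted after a only, so after 4 of 12. But b is followed by whether it was easier or harder and why, and c by whether the faces help and why. Some question on ease, with a reason, therefore follows all 12.

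**What rotation would cost.** If all six orders were used about equally, the word scale would come first in 2 of 6 (16 × 2/6 = 5.3, so 5 or 6 children) and before any faces in 3 of 6 (16 × 3/6 = 8). Each order would have 16/6 = 2.7 children, so 2 or 3.

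**The case against.** On 2c, the best defence is that the wording was evidently carried over from 1c, that the guide need not be read verbatim, and that an experienced interviewer would notice. Older children are also told to "tell me what you are thinking about when you decide on an answer", and every child is asked about a face: "what words would you use? What feeling does the face make you think of? Why". This softens the consequence. It does not correct a written trigger that names the wrong item, and the think-aloud instruction is absent from the 5-7 module. The pattern counts are not an error rate: how often the rule misfires depends on how children answer, which the documents cannot tell us.

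On order, more of the defence stands. This is a small qualitative study, the reasons are collected, and showing plain words before illustrated words is defensible, because faces shown first would prime the word scale. Several stronger readings are tempting but not supported:

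- That the easiest answers decide the format. No section makes them a selection rule or an endpoint, and reasons are asked for after each format separately.
- That only the word scale is probed for difficulty. The count of 4 in 12 concerns one wording; ease is raised after all 12 presentations.
- That the order used would be lost. Section 3.1 provides for audio recording, transcripts and field notes, so it is recoverable.
- That the order favours faces. Neither size nor direction is known. Any computed chance of a majority for faces would rest on an assumed recency effect and a majority rule that the documents do not contain.
- That full rotation is required. With 2 or 3 children per order it would support no order-specific conclusion, and it gives up unprimed readings of the word scale.

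**Conclusion.** The 2c trigger is wrong as written in both age modules. It misses a words-versus-faces discrepancy in 12 of 64 possible answer patterns and probes a consistent answer in another 12. The missed discrepancies matter more, since an unneeded follow-up costs only a little time. This assumes that the rule is applied as printed and that the follow-up at 2c is meant to do what it does at 1c.

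The fixed order is a minor point of interpretation. The easiest answers, the liked-best answers (ages 8-11 only) and the words-versus-faces comparison cannot separate format from position and prior exposure. The format-specific reasons mitigate this in part, but no probe asks about order and section 5 does not alert the reader to it.

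**What to change.** 1. In Appendix C, change 1a to 2a in the conditional follow-up at 2c, in both the 5-7 and the 8-11 module. Leave the 1c follow-up as it is. This is a wording change in two places with no added participants or interview time. Section 6.1 has data-collection materials reviewed by the IRB, so the corrected guide should go through that route.

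2. Add a sentence to section 5 saying that all children are scripted the formats in one order, so stated preferences and words-versus-faces agreement may partly reflect position and prior exposure. In section 4, say that no response format will be chosen on the easiest or liked-best answers alone. This costs two sentences.

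3. Optional: a simple recorded rotation of the formats. It would need re-orderable item sheets and rewording of probes that presuppose the sequence, such as "Is this question the same or different than the one we just talked about" and the follow-up keyed to a. Using all six orders, children meeting the word scale before any faces would fall from 16 to 8, and those meeting it first from 16 to 5 or 6. Preference should then be read alongside position descriptively only.

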## **3 RESEARCH METHODOLOGY**

### **3.1 Study Design**

This cross-sectional, qualitative study will involve up to 16 child and caregiver dyads (total of 32 participants). Specifically, two iterative rounds of cognitive debriefing (targeting 8 dyads per round) will be conducted at two different qualitative research facilities that specialize in recruitment and the conduct of qualitative studies. Given the pediatric population, the proposed methods and procedures have been developed based on the recommendations provided by the International Society for Pharmacoeconomics and Outcomes Research (ISPOR) Task Force for Good Practices for the Assessment of Children and Adolescents (Matza et al., 2013). Specifically, the adult ease of use items will be modified to incorporate language appropriate for children. In addition, varying modes of administration will be assessed, including interview administration for children aged 5 to 7 years and for those who are reported by the caregiver to not be able to or to have difficulty reading. Draft pediatric and caregiver items are provided in Appendix B.

Given the age of the pediatric participants, caregivers will also be included in the interview room; however, the caregiver will be asked to sit behind the child and remain silent during the interview in order to avoid influencing the child's responses.

The interviews will be conducted by two experienced interviewers from RTI-HS. One interviewer will take primary responsibility for leading the interview while the second records detailed field notes. Field notes will incorporate both the verbal exchange between the participant and interviewer and the nonverbal cues that may influence interpretation of the data, particularly important in interviews with children. A standardized, semistructured discussion guide (Appendix C) will be used to ensure consistency of data collection across interviews. Each interview will last approximately 45 minutes. All interviews will be audio recorded and transcribed by a medical transcriptionist for use in preparing a written summary report.

Each interview will be conducted at a research facility in Raleigh, NC, or Detroit, MI; both facilities specialize in the recruitment of participants and facilitation of qualitative studies (e.g., hosting, recording).

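### Appendix C keys the follow-up question under item 2c to item 1a (ease of use) instead of 2a (puffs left, words only), so some children who change their answer are not asked why

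*Combined protocol and SAP*

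**What the plan says.** Appendix C puts each pediatric question to the child in three forms: a word-only four-level scale (1a, 2a), a yes/no form (1b, 2b) and the four levels shown with faces (1c, 2c). Items 1a to 1c ask how easy the inhaler is to use. Items 2a to 2c ask how easy it is to tell how many puffs remain.

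Under 1c, the prompt asking why the child chose the circled answer carries the condition "Only ask if a different response from 1a was chosen". The same condition, still naming 1a, is printed under 2c. Both statements hold in the section for ages 5-7 and in the section for ages 8-11.

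The two sections open differently. For ages 5-7 the instruction reads "Then I will ask you to choose the answer that matches what you thought about using the", followed by the child's own name for the inhaler. For ages 8-11 the child is told "I would also like to tell me what you are thinking about when you decide on an answer".

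On how the guide is to be used, Section 3.1 says "A standardized, semistructured discussion guide (Appendix C) will be used to ensure consistency of data collection across interviews", while the note at the head of Appendix C says "The guide is not intended to be followed in a verbatim question format".

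**The concern.** The condition under 1c has a clear purpose: if a child answers the same question one way in words and another way with faces, find out why. Under 2c the equivalent comparison is with 2a, which has the same stem and the same four levels. Comparing 2c with 1a compares answers to two different questions, and nothing in the protocol gives a reason for doing so. The identical wording in both sections suggests that it was carried over from 1c.

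What is at stake is evidence on response format. Appendix B lists the three forms as alternatives, and Section 4 says the first set of interviews should detect early problems with wording or response choices. A child's reason for changing an answer between words and faces bears directly on that.

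**Working it through.** There is no planned figure to reproduce, so the check is on the routing logic.

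**Inputs (Appendix C, both age sections).** Let a be the answer to 1a, b the answer to 2a and c the answer to 2c, each on four levels (very easy, easy, hard, very hard).

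- Printed rule under 2c: ask why if c ≠ a.
- Matching rule, parallel to the one under 1c: ask why if c ≠ b.

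**Enumeration.** There are 4 × 4 × 4 = 64 patterns of (a, b, c).

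| Case | Patterns | Prompt missed (c = a, c ≠ b) | Unnecessary prompt (c = b, c ≠ a) | Routed correctly |
|---|---|---|---|---|
| a = b | 4 × 4 = 16 | 0 | 0 | 16 |
| a ≠ b | 12 × 4 = 48 | 12 | 12 | 24 |
| Total | 64 | 12 | 12 | 40 |

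The matching rule asks in 64 − 16 = 48 patterns. The printed rule also asks in 48, but 12 of those are unnecessary, and it misses 12 of the 48 in which the word and faces answers to the puffs-left question really differ. With 2a in the condition, both error counts are zero.

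**Example.** Take a child who answers easy to 1a and hard to 2a. If 2c is easy, the child has changed answer on the same question but is not asked why, because 2c equals 1a. If 2c is hard, nothing has changed, yet the child is asked.

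**Whether another prompt recovers the reason.** For ages 5-7 there are four prompts under 2c: the conditional one and three that are always asked. Those three are "Do you think the faces make it easier to answer the question? Why", a prompt on what a chosen face conveys, and "Which of the three questions that I asked you was the easiest to answer? Why". They cover response format in general, but none asks why this 2c answer was given, and the opening instruction does not ask the child to think aloud. For ages 8-11 there are three prompts under 2c, one conditional and two always asked, plus a closing look-back over the three forms. The general think-aloud request there can still bring out the reason, so the loss is smaller, though not zero.

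**Number of children.** The documents give no distribution of answers and no target number for ages 5-7; the screener (Appendix D) sets only a soft limit of 2 children aged 10 or 11. The number affected therefore cannot be estimated. It cannot exceed the number, among up to 16 children (Section 3.1), whose 1a and 2a answers differ, and a missed prompt also requires 2c to equal 1a.

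**The case against.** The strongest reply is that this is a one-character slip in a guide that is not meant to be read out word for word. Section 3.1 provides two experienced interviewers, one leading and one taking field notes. After 2a, as after 1a, the section for ages 5-7 carries the note "Interviewer notes the response selected by the child", so the interviewer has the right answer to hand and, knowing the purpose from 1c, would probably make the right comparison. The child has also just been asked about the reasons for the 2a and 2b answers, and the words-versus-faces comparison is correctly keyed under 1c.

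Much of this stands, and it is why the point is minor. Two things remain. The prompts after 2a and 2b precede 2c, so they cannot explain a change made at 2c. And a guide intended to make data collection consistent should not depend on each interviewer noticing and overriding a printed condition. The noted 2a answer lets a change be seen afterwards, but a reason that was never asked for may not be recoverable.

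It is also fair to say that the pattern counts weight implausible and plausible patterns alike, so 12 of 48 must not be read as a 25% miss rate. Nor does age map exactly to section: Section 3.1 and Appendix B allow interviewer administration for older children with reading difficulty. The statement about ages 5-7 is an inference from the wording of the two sections, not something the protocol states.

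**Conclusion.** The concern holds, as a minor error. The condition under 2c names the wrong item in both age sections. It does no harm when a child's 1a and 2a answers agree. When they differ, one of the four possible 2c answers loses the prompt and one draws a harmless extra question; only the first is a real loss. That loss falls mainly on children taken through the section for ages 5-7. The conclusion assumes that the condition is followed as printed. The primary and secondary endpoints, the sample size and the planned descriptive summaries are unaffected.

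**What to change.** Before the first set of interviews, change 1a to 2a in the condition under item 2c in both age sections of Appendix C. Leave the condition under 1c as it is. For ages 5-7 the comparison needs no new recording, since the 2a answer is already noted. The cost is one item label in two places, plus submission of the corrected guide to the IRB, which under Section 6.1 reviews all data-collection materials.
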